7.4 DIETARY AND LIFESTYLE RESTRICTIONS

Not applicable.

7.5 OVERDOSE

Overdose is defined as the accidental or intentional administration of any dose of a product that is considered both excessive and medically important. An overdose that does not result in any adverse signs or symptoms should not be considered an AE. The effects of any potential overdose with QIV have not been studied.

8 STUDY PROCEDURES AND VISIT SCHEDULE

8.1 CLINICAL PROCEDURES

The clinical procedures that will be conducted during this study related to the evaluation of population demographics, efficacy, immunogenicity, and safety are provided in Table 8.1-1 below. Refer to the Laboratory Manual for detailed instructions on how the assessments should be performed.

Table 8.1-1 Clinical Procedures: Demographics and Safety Evaluation

Assessment	Description
Demographics	Date of birth, age, sex, race and ethnicity
Medical history	Relevant medical history is defined as: any current medical condition ongoing at the time of signing ICF, or any recent or past medical history, which in the opinion of Investigator would potentially have an impact on subject's eligibility, study safety or immunogenicity outcomes. Relevant medical history can also include any medical history that contributes to the understanding of an AE that occurs during study participation, if it represents an exacerbation of an underlying disease/preexisting problem. Influenza vaccination history, and current/concomitant therapies should also be recorded.
Physical examination	Targeted physical examination as clinically indicated following the collection of medical history
Measurements	Body temperature (°F and °C) using axillary measurement. Body weight (kg)
Vaccination	Administration of one or two doses of Study Vaccine.
Blood sample	A volume of at least 3 mL of blood will be collected at each visit (Visit 1 and Exit Visit). Total volume of blood collected per subject is at least 6 mL. Blood will be centrifuged according to laboratory procedures and transported by courier from investigational sites to the central sample management laboratory.

Immunogenicity	Serum analyzed for the presence of binding antibodies specific to Study Vaccine by hemagglutination inhibition assay.
Virological test (if ILI case definition met)	
In the event of an influenza-like illness (ILI) between Visit 1 and Exit Visit nasal and throat swabs may be collected as follows:
 
 • Nasal swab from the right nostril; • Nasal swab from the left nostril; and • Throat swab. 
Nasal and throat swab specimens will be analyzed by the central analytical laboratory for laboratory confirmation of influenza A/B by reverse transcriptase polymerase chain reaction (RT-PCR).

The timing and frequency of all clinical procedures are described in the [Schedule of Assessments](#). Refer to the Laboratory Manual for details about the collection, storage, handling and transportation of biological specimens.

8.2 RETENTION OF SAMPLES

Serum retention samples will be obtained at Visit 1 and Visit 2 or 3. Retention samples will be stored at [REDACTED], [REDACTED] in a secure facility under appropriate storage conditions for a maximum of 5 years after sign-off of the Clinical Study Report, after which retention samples will be destroyed. Retention samples may be used to perform additional serological analysis on the entire study population (or population subsets), using modified HI assays, or different assays types, including but not limited to viral microneutralization assays. Such additional assay analyses may be requested by regulatory agencies, or may be conducted by the Sponsor if there is a need for additional assay work to assist with the interpretation of the original study assay results, or to further characterize the immune response to influenza vaccination in the study population. Additionally, retention samples may be used to inform the development, performance, validation, or testing of new or modified assays to assess the serological impact of influenza vaccination. No form of genetic testing of the subject population will be performed at any time.

8.3 CONCOMITANT THERAPIES

All drugs and/or procedures (including any physician-prescribed dietary supplement or vitamin), currently being administered to a subject at the time of signing informed consent, and which continue to be taken in addition to the Study Vaccine during the Active Study Period, are regarded as concomitant therapies and must be documented as such in the eCRF. Concomitant medications that are being taken at the time of study enrollment should be initially recorded, and the reason for medication being taken should be recorded. At subsequent visits, any concomitant medications used during the active study period (from Day 1 until Exit Visit) should be recorded, and the reason for medication should be recorded. After the active study period, it is no longer necessary to routinely seek information on concomitant medications. However, if an SAE occurs after the Exit Visit, any medications

taken prior to and at the time of the SAE (whether or not related to the SAE) should be recorded.

8.4 VISIT SCHEDULE

The timing and frequency of the study visits are described in the [Schedule of Assessments](#). Time windows for all assessments are detailed in Table 8.4-1 below.

Table 8.4-1 Time Windows for Assessments

Visit/Procedure	Time window (relative to scheduled visit/procedure)
Screening (Day -7 to 1)	Not applicable.
Visit 1 (Day 1)	≤ 7 days after screening
Phone call (Day 3)	+ 2 days
Visit 2 (Day 29)	+ 4 days
Phone call (Day 3 after the 2 nd dose)	+ 2 days
Visit 3 (Day 29 after the 2 nd dose)	+ 4 days
Phone call (90 days after the last dose)	+ 7 days
Phone call (180 days after the last dose), End of Study	+ 7 days
ILI (if necessary)	Target for ≤ 3 days after onset of the symptoms meeting the case definition of an ILI.
Cellulitis-like reaction (if necessary)	Target for within 24 hours after onset of the symptoms meeting the cellulitis-like reaction criteria (or ≤ 3 days if on a weekend).

8.4.1 Screening

Parent(s) or legally appropriate representative must provide written informed consent before any study-specific assessments or procedures are performed. Written informed consent must be signed by the subject's parent or legally appropriate representative and the medically-qualified Investigator (MD or Doctor of Osteopathy) obtaining the consent. Written informed consent is not required for assessments or procedures performed according to standard of care (eg, for diagnosis or treatment); results from such assessments may be used in the determination of study eligibility.

A screening examination should be performed up to 7 days before the intended date of dosing (Day 1). If a potential subject was not enrolled into the study within 7 days of the first

screening visit, the potential subject may attend a second screening visit (for a maximum of two screening visits per subject). In the event that a potential subject is screened twice, a new subject number will be assigned and all screening assessments must be repeated at the second screening visit.

Subjects who complete all of these assessments and who fulfil the eligibility criteria (ie, eligible subjects) will be enrolled into the study. If the subject is not eligible for the study, the primary reason for screen failure must be entered in the eCRF.

Subjects will be recruited through generic advertisements or Institutional Review Board-approved study-specific advertisements. For those potential subjects interested in participating in the study, an appointment will be scheduled to allow informed consent to be obtained. Written informed consent can be provided by parents(s)/guardian(s) of subjects up to 1 week prior to the day of vaccination. The subject's age and influenza vaccination history will determine the dose and dosing regimen (a single vaccination or a two-vaccination regimen administered 28 days apart). The first vaccination will be administered at Visit 1 (Day 1) and the second vaccination, if scheduled will be administered at Visit 2 (Day 29+4).

8.4.2 Treatment Period

Visit 1 (Day 1) – Day of Vaccination (Either 1 or 2 Dose Schedule)

Informed Consent: A parent/guardian of the subject must provide written informed consent prior to any study-related procedures. Subjects with parent/guardian informed consent will be issued the next available unique subject number by IRT, including those who prove to be screen failures.

Prevaccination: The following assessments will be performed and documented in the source notes:

- A review of the subject's medical history, including concomitant medications, vaccination history (including influenza vaccination), and documentation of any relevant medical history;
- Targeted physical examination as clinically indicated following the collection of medical history;
- Subject's axillary temperature and body weight;
- A review of the subject's eligibility according to the Inclusion/Exclusion criteria
- Collection of at least 3 mL blood sample.

Subjects who complete the above assessments and who fulfill the inclusion/exclusion criteria will be eligible for randomization. Study vaccine will be assigned via IRT.

Vaccination: As per the US ACIP guidelines for seasonal influenza vaccination, the subject's age and influenza vaccination history determines the dose and dosing regimen (a single vaccination or a two-vaccination regimen administered 28 days apart). The first vaccination will be administered at Visit 1 (Day 1) and the second vaccination, if scheduled, will be administered at Visit 2 (Day 29 + 4). The Investigator/delegate will administer the study vaccine according to the randomization code into the deltoid region of the arm or into the anterolateral aspect of the thigh, by intramuscular injection. If vaccination into the arm is selected, the injection will be administered where possible into the contralateral arm to which the blood sample was drawn.

Subjects will receive the following dose depending upon their age at the time of administration of the first dose of Study Vaccine:

Cohort A	6 months through 35 months of age	0.25 mL
Cohort B	36 months through 59 months of age	0.5 mL

Postvaccination:

- Subjects will be observed for at least 30 minutes after vaccination for signs of an anaphylactic reaction. Appropriate medical treatment will be readily available in case of emergency.
- Parent(s)/guardian(s) will be issued with a digital thermometer and Local Reaction Measurement Card, and provided with electronic access to the 7-Day Diary (for recording solicited AEs), the Other Body Symptoms Diary (for recording unsolicited AEs), and the Medications Diary (for recording all concomitant medications). The 7-Day Diary will be completed on the day of vaccination and for the subsequent 6 days following vaccination (total of 7 days). The Other Body Symptoms Diary and the Medication AE Diary will be completed on the day of vaccination until the next study visit.
- Parent(s)/guardian(s) will be reminded how to measure axillary temperature and record their child's temperature at the same time each evening, in addition to completing the diaries.
- Parent(s)/guardian(s) will be instructed to contact the Investigator/delegate immediately if the subject experiences any signs or symptoms with grade 3 intensity.
- Parents will be educated on how to recognize the signs/symptoms of an ILI and will be instructed to contact the investigator/delegate immediately if the subject experiences any signs or symptoms of an ILI from Day 1 until the Study Exit Visit.
- An appointment will be made for each subject to return to the clinic 28 + 4 days after Visit 1 (Day 29 +4).

8.4.3 On-study Period

Diary Reminder Telephone Call (Day 3 + 2):

Sites will contact parent(s)/guardian(s) of subjects by telephone between Days 3 and 5 inclusive, to check that the electronic diaries are being completed daily, and to address any questions on how to complete them correctly.

Visit 2, Study Exit Visit (Single Dose Schedule) Day 29 + 4

Subjects who are scheduled to receive a single dose of study vaccine according to the previous immunization history, will exit the study at this visit.

The following will be undertaken and recorded at the Exit Visit:

- Review of the electronic diary entries;
- Assessment of the occurrence of any AEs, SAEs and AESIs;
- Targeted physical examination as clinically indicated;
- Collection of at least 3 mL blood sample.

OR

Visit 2, Second Vaccination (Two-Dose Schedule) Day 29 + 4

Subjects who are scheduled to receive 2 doses of study vaccine will require a second dose of study vaccine at this visit.

Prevaccination:

The following will be undertaken and recorded prior to administration of the second dose of study vaccine:

- Review of the electronic diary entries;
- Assessment of the occurrence of any AEs, SAEs and AESIs;
- Subject's ongoing eligibility will be reviewed;
- Targeted physical examination as clinically indicated;
- Subject's axillary temperature.

Vaccination:

Subjects will be injected following the same guidelines as for the first dose.

Subjects who are scheduled to receive 2 doses of study vaccine and who turn 36 months of age between the two study vaccinations will receive a second dose of 0.25 mL of study vaccine.

Postvaccination:

- Subjects will be observed for at least 30 minutes after vaccination for the signs of an anaphylactic reaction; Appropriate medical treatment will be readily available in case of emergency.
- Parent(s)/guardian(s) will be reminded to complete the 7-Day Diary entries for the day of the second vaccination and for the subsequent 6 days following vaccination (total of 7 days), and to continue recording unsolicited AEs in the Other Body Symptoms Diary and concomitant medications in the Medications Diary from the day of the second vaccination until the Study Exit Visit.
- Parent(s)/guardian(s) will be reminded on how to measure axillary temperature and record their child's temperature at the same time each evening, in addition to completing the diaries.
- Parent(s)/guardian(s) will be instructed to contact the Investigator/delegate immediately if the subject experiences any signs or symptoms with grade 3 intensity.
- Parent(s)/guardian(s) will be reminded on how to recognize the signs/symptoms of an ILI and will be instructed to contact the investigator/delegate immediately if the subject experiences any signs or symptoms of an ILI from Visit 2 until the Study Exit Visit.
- An appointment will be made for each subject to return 28 + 4 days post-Dose 2 for a Study Exit Visit (Day 29 + 4 days after the second vaccination).

Diary Reminder Telephone Call (Day 3 + 2 after the second vaccination):

Sites will contact parent(s)/guardian(s) of subjects by telephone between Days 3 and 5 inclusive after the second vaccination, to check that the diaries are being completed daily, and to address any questions on how to complete them correctly.

Visit 3, Study Exit Visit (Two-dose Schedule)

The Study Exit Visit for the Two-dose Schedule will occur 28 + 4 days after the administration of the second dose of Study Vaccine (Visit 2).

The following will be undertaken and recorded at this study visit:

- Review of the electronic diary entries;
- Assessment of the occurrence of any AEs, SAEs and AESIs;
- Targeted physical examination as clinically indicated;
- Collection of at least 3 mL blood sample.

Unscheduled Visit - Influenza-like Illness (ILI) Visit

Subjects reporting signs/symptoms of an ILI between Visit 1 and Study Exit Visit (Visit 2 or Visit 3) will be asked to attend an additional clinic visit within 72 hours of the symptoms meeting the case definition of an ILI, for confirmation of the ILI.

The criteria for an ILI are as follows:

- Elevated axillary temperature of $\geq 99.5^{\circ}\text{F}$ ($\geq 37.5^{\circ}\text{C}$) or a clear history of fever or chills; and
- At least one respiratory symptom, including sore throat, cough, wheezing, rhinorrhea/rhinitis; and
- At least one systemic symptom, including myalgia, headache, malaise and fatigue, diarrhea, nausea and/or vomiting, loss of appetite, and irritability.

To qualify as symptoms for the ILI case definition, symptoms should be either new, or for chronic symptoms, changed in severity or nature.

Influenza antiviral drugs (Symmetrel [amantadine], rimantadine, Tamiflu [oseltamivir] or Relenza [zanamivir]) should not be prescribed from any source until after the ILI assessment visit and the collection of respiratory specimens if indicated.

The site should perform an assessment to attempt to confirm a postvaccination ILI at the time of the ILI-assessment visit (the subject's temperature and clinical symptoms should be assessed). Additionally, the site may also confirm a postvaccination ILI through review of the AE diaries and/or illness history reported verbally by the subject at a time prior to the ILI visit. Information related to confirmation of a postvaccination ILI should be recorded in the subject's source notes.

Upon confirmation that the ILI case definition is met, the subject's temperature will be assessed and attempts will be made to diagnose influenza viral infection by obtaining nasal and throat swab specimens. These will be analyzed for laboratory confirmation of influenza A and/or B by Reverse Transcriptase Polymerase Chain Reaction (RT-PCR).

Laboratory confirmation is more likely for specimens collected within approximately 3-4 days of illness onset, but nasal and throat swabs should be collected if the ILI assessment visit occurs up to 7 days after illness onset, to try to identify as many cases of laboratory confirmed influenza infection as possible. After 7 days following illness onset, the Investigator may choose whether to collect nasal and throat swabs, based on their clinical judgement of the potential value of testing specimens due to ongoing ILI symptoms.

Refer to the study-specific Nasal and Throat Swab Specimen Collection Instructions, for further details on collection, storage, handling and transportation of the nasal and throat swab specimens to the laboratory.

Unscheduled Visit – Cellulitis-like Reaction

Subjects reporting signs/symptoms of a Cellulitis-like Reaction between Day 1 and Study Exit Visit will be asked to attend an additional clinic visit within 24 hours (up to 3 days if on a weekend) of the symptoms meeting the definition of a cellulitis-like reaction.

The criteria for a Cellulitis-like Reaction are concurrent presence of all three of the following:

- Grade 3 injection site pain;
- Grade 3 injection site erythema;
- Grade 3 injection site induration.

Investigational site staff attending the subject will confirm if he or she meets or has met the cellulitis-like illness case definition postvaccination according to reported symptoms and, if applicable, will perform other clinical investigations as relevant according to routine clinical practice. Additionally, investigational site staff will assess for the presence of ulceration, abscess, or necrosis at the injection site, which will inform the application of study enrollment halting rules. In the event of a possible cellulitis-like reaction, sites should identify a local laboratory to perform any laboratory analyses to investigate, confirm, and manage any confirmed cellulitis-like reactions, and document any results in the source notes.

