14.3 IMPLEMENTATION OF THE PROTOCOL / PROTOCOL AMENDMENT(S)

With the exception of medical emergencies, no changes or deviations in the conduct of the signed protocol will be permitted without documented approval of Seqirus and the IRB. In the event of a medical emergency, the Investigator at the study site will institute any medical procedures deemed appropriate. However, all such procedures must be promptly reported to the Seqirus Medical Monitor and the IRB.

Modifications to the protocol that may affect subject safety or the way the study is to be conducted will be documented in a protocol amendment, which must be approved by the IRB.

Administrative changes to the protocol, defined as minor corrections and/or clarifications that have no effect on the way the study is to be conducted, will not require IRB approval, but will be submitted to the IRB for their information.

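### Protocol 8.4.3 defers four influenza antivirals until after the ILI visit and any indicated swab, with no stated cap and no provision for necessary non-emergency treatment to go first

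*Protocol*

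**What the plan says.** For an ILI between Visit 1 and the Study Exit Visit, protocol 8.4.3 names amantadine, rimantadine, oseltamivir and zanamivir and says that they "should not be prescribed from any source until after the ILI assessment visit and the collection of respiratory specimens if indicated". SAP 3.3.3 carries the identical sentence.

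On the timing of the visit:

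- Families "will be asked to attend an additional clinic visit within 72 hours of the symptoms meeting the case definition of an ILI" (protocol 8.4.3).
- Table 8.4-1 in protocol 8.4 labels this a target, of at most 3 "days after onset of the symptoms meeting the case definition of an ILI".
- Parents are "instructed to contact the investigator/delegate immediately if the subject experiences any signs or symptoms of an ILI" (protocol 8.4.2).
- If the visit is later, "nasal and throat swabs should be collected if the ILI assessment visit occurs up to 7 days after illness onset". Beyond that, "After 7 days following illness onset, the Investigator may choose whether to collect nasal and throat swabs" (both protocol 8.4.3).

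The stated aim of the swab timing is "to try to identify as many cases of laboratory confirmed influenza infection as possible".

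On exceptions, protocol 14.3 says: "In the event of a medical emergency, the Investigator at the study site will institute any medical procedures deemed appropriate". Protocol 14.4 allows an investigator to deviate to remove an immediate hazard, and otherwise grants no prospective waivers. Protocol 4.2.1, on withdrawal, states that the subject's interests come before the study's. Protocol 7.2 permits every therapy that 7.3 does not list, and 7.3 does not list influenza antivirals.

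**The concern.** What releases the antiviral is an event, the study visit with its swab where indicated. It is not a time limit or a clinical judgement. If the visit is late or does not happen, nothing in the text ends the deferral. The phrase about any source also reaches beyond study staff, to a family doctor or an emergency clinic.

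The participants are children aged 6 to 59 months, enrolled during an influenza season. Followed as written, the sentence makes treatment that a clinician considers necessary wait for a procedure whose purpose is case confirmation, which is a study interest. At stake are participant welfare and clear instructions to sites. The validity of the noninferiority comparison is not in question.

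**Working it through.** No sample size, power or error rate is involved, and the plan states no figure to reproduce. The check is a reading of the texts side by side, followed by one piece of arithmetic on the visit timing.

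**Step 1: what ends the deferral.** Protocol 8.4.3 ties prescribing to completion of the visit and any indicated swab. The 72 hours in 8.4.3 and the 3 days in Table 8.4-1 apply to the visit, and the table calls them a target. Neither is a limit on how long treatment may be withheld. After day 7 the investigator has discretion over the swab, but not, on the wording, over the antiviral, which still waits for the visit.

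**Step 2: whether another provision releases it.**

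| Provision | What it covers | Reaches non-emergency treatment before the visit? |
|---|---|---|
| Protocol 14.3 | Medical emergencies | No |
| Protocol 14.4 | Immediate hazards; no prospective waivers otherwise | No |
| Protocol 4.2.1 | General priority of the subject's interests, in the withdrawal section | Not explicitly |
| Protocol 7.2 and 7.3 | Antivirals permitted because they are not listed | Silent on timing; no reference to 8.4.3 |

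A specific timing instruction in 8.4.3 therefore stands beside general permissions that do not mention it. By contrast, 7.3 bars prophylactic antipyretics and then expressly permits antipyretics to treat adverse events. The antiviral sentence has no matching clause.

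**Step 3: how far past the target a visit allowed for in the text could fall.** The two clocks start at different points: the target runs from meeting the case definition, the 7 days from illness onset.

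- Target: 3 days = 72 hours after the case definition is met (protocol 8.4 and 8.4.3).
- Visit at which swabs are still expected: up to 7 × 24 = 168 hours after onset (protocol 8.4.3).
- Let the case definition be met *d* days after onset. The documents do not give *d*, so it is an assumption.
- Time of a day-7 visit past the target = 168 − 72 − 24*d* hours.

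| *d* (days) | Calculation | Hours past target |
|---|---|---|
| 0 | 168 − 72 − 0 | 96 |
| 1 | 168 − 72 − 24 | 72 |
| 2 | 168 − 72 − 48 | 48 |
| 3 | 168 − 72 − 72 | 24 |
| 4 | 168 − 72 − 96 | 0 |

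A day-7 visit can therefore be exactly on target (*d* = 4) or four days late (*d* = 0). Because visits after day 7 are also allowed for, the text yields no maximum.

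**The case against.** The strongest reply is that little is left after the existing text is applied. The instruction is worded as a should-not, antivirals are not on the prohibited list, and no analysis-set consequence is stated for taking one early. Emergencies and immediate hazards are exempt. The principle in 4.2.1 is unqualified in its wording, even though it sits under withdrawal. Parents are told to call immediately, so a site can often arrange the visit promptly. The order also serves a stated purpose: confirmed influenza cases are excluded from the Evaluable Population (protocol 11.2.3, SAP 3.5.3), from which the primary Per-Protocol Population is drawn.

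Much of this stands as to extent. It narrows the point to a child who is not an emergency, whose clinician wants to treat before the visit. It does not remove the point. The sentence in 8.4.3 is the only instruction on antiviral timing, and none of the other provisions says that treatment may come first.

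A reader might infer more than the documents support:

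- *That late visits are planned.* They are not. The section says when a swab is still worth taking if a visit is late; the intended timing is 72 hours.
- *That treatment is typically delayed by two to four days beyond the target.* The table above runs down to zero, and it describes only a day-7 visit. Nothing in the documents says how often such visits occur.
- *That children would be harmed.* The documents give no data on antiviral timing and outcome.

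**Conclusion.** The concern holds as a gap in the protocol's wording on participant welfare, and it is worth correcting because the correction is cheap. The deferral has no stated cap and no allowance for non-emergency treatment that a clinician judges necessary.

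The number of children affected and the usual length of delay cannot be estimated from the documents. The one available figure, 0 to 96 hours past target for a day-7 visit, rests on the case definition being met four to zero days after onset. No size of harm is claimed. A reader might also infer a bias in the eight co-primary endpoints; nothing in the documents supports that, and none is claimed.

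The consent pages and the separate swab collection instructions were not available and might contain guidance to sites, so the conclusion is limited to the protocol and SAP text.

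**What to change.** After the antiviral sentence in protocol 8.4.3, add:

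> Antiviral treatment that the treating clinician judges necessary must not be delayed for the ILI assessment visit or specimen collection; specimens should still be collected at the ILI visit, and the antiviral and its start date recorded as a concomitant medication.

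The protocol sentence is the one that guides sites. Repeat it in SAP 3.3.3 only so that the two texts agree. Leave protocol 7.2 and 7.3 alone: a cross-reference there would put a restriction into sections that are now permissive.

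Because the change bears on subject safety, it needs an IRB-approved amendment under protocol 14.3. It adds no patients and no visits, and concomitant medications are already recorded under protocol 8.3.

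The downside is that RT-PCR yield may be lower in children treated before the swab. Some influenza cases might then go unconfirmed and stay in the Evaluable Population. The documents do not allow the size of this to be estimated.
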